9. MULTISITE REGULATORY CONSIDERATIONS

The Stanford Cancer Institute Data and Safety Monitoring Committee (DSMC) will be the monitoring board for this study, please refer to the Data and Safety Monitoring Committee SOP for more information.

11.1 Monitoring plan

The Stanford Cancer Institute Data and Safety Monitoring Committee (DSMC) will be the monitoring entity for this study. The DSMC will audit study-related activities approximately once per year to determine whether the study has been conducted in accordance with the protocol, local standard operating procedures, FDA regulations, and Good Clinical Practice (GCP). This may include review of the following types of documents participating in the study: regulatory binders, case report forms, eligibility checklists, and source documents. In addition, the DSMC will regularly review protocol deviations from all sites associated with the research to ensure the protection of human subjects. Results of the DSMC audit will be communicated to the IRB and the appropriate regulatory authorities at the time of continuing review, or in an expedited fashion, as needed.

The Stanford Cancer Institute research team will conduct bi-annual audits of sub-site enrollment and regulatory compliance. This will include a review of one subject enrolled in that time period including case report forms, eligibility checklists, source documents and regulatory binders. If no subjects have been enrolled in this time period, the audit will be skipped until the next cycle. The research team will also review protocol deviations and communicate findings with the DSMC and IRB as appropriate.

11.2 Protocol Review and Amendments

The protocol, the proposed informed consent and all forms of participant information related to the study (e.g. advertisements used to recruit participants) will be reviewed and approved by the Stanford IRB and Stanford Cancer Institute Scientific Review Committee (SRC). Any changes made to the protocol will be submitted as a modification and will be approved by the IRB prior to implementation. The Protocol Director will disseminate the protocol amendment to all participating investigators. Investigators will be expected to obtain IRB approval within 90 days for all amendments.

11.3 Data management

The Protocol Director, or his/her designee, will prepare and maintain adequate and accurate participant case histories with observations and data pertinent to the study. Study specific Case Report Forms (CRFs) will document treatment outcomes for data analysis. Case report forms will be developed using the REDCap database system and will be maintained by study personnel under the direction of the protocol director. CRFs will be kept in a locked office, only accessible to the research team.

A chart with all of the relevant research patient information will be maintained for each patient at each institution, and the patient charts may be reviewed by Stanford for yearly audits.

Study data will be collected and managed using REDCap (Research Electronic Data Capture). REDCap is a secure, web application designed to support data capture for research studies. It provides user-friendly, web-based case report forms, real-time data entry validation (e.g. for data types and range checks), audit trails and de-identified data export mechanism to common statistical packages (SPSS, SAS, Stata, R/S-Plus). The system was developed by a multi-

institutional consortium which includes Stanford University and was initiated at Vanderbilt University. The database is hosted at the Stanford University School of Medicine secure data center. The system is protected by Secure Socket Layer (SSL) encryption and a strong web based authentication system. Data collection is customized for each study or clinical trial based on a study-specific data dictionary defined by the research team with guidance from the Stanford Center for Clinical Informatics REDCap administrator. Every personnel in the different sites is given access to only their specific site's "Data Access Group" and can only see and enter information for their patients. The Stanford research team will manage this access.

For patients randomized on the app arm of the study, some of their data will be captured via the VIbrent Health application. Vibrent Health has been deploying and managing solutions in highly regulated, highly secure, highly sensitive environments. Vibrent Health has supported and accredited solutions for the National Institute of Health (NIH), the US Army, commercial and military medical treatment facilities and hospitals. We understand the compliance requirements for these industries and the business requirements to protect the sensitive data that these businesses contain. Vibrent Health currently uses Cyber Secure Amazon AWS Cloud infrastructure to host the Vibrent Platform. Amazon AWS Cloud provides compliance with various Federal regulations that impact privacy and security requirements. AWS Cloud is FedRAMP and FISMA certified and provides many other compliances and certifications such as HIPAA, SOC 1/2/3, PCI DSS Level 1, ISO 27001 and others. AWS Data centers are housed in nondescript facilities and are not open to the public.

Vibrent Coaching Platform (VCP) App is based on a three-tier architecture consisting of web, application and data tiers. The data tier consists of an Amazon Web Services RDS Aurora Multi zone deployment. The database contains all data interactions with the patients. The data tier is deployed upon AWS Aurora product which is Amazon's custom MySQL offering.

11.4 Study Documentation

The Protocol Director and participating site investigators must maintain adequate and accurate participant case histories with observations and other data pertinent to the study. Original source documents should be transcribed to REDCap in a timely manner and used to communicate study data to the lead site. Source documents include hospital records, clinical charts, laboratory and pharmacy records, and recorded electronic data. Original source documents should be kept by each site, an must be provided to the lead site when requested.

Participating Center's PIs will be responsible for maintaining the clinical protocol and subjects' study charts, assuring that consent is obtained and documented, and reporting the status of the trial in continuing renewals submitted to their IRB and trial monitoring group(s) as per their facility protocol. Prior to a subsite's start of enrollment, each subsite will be required to attend a teleconference where relevant Stanford research SOPs and documentation will be reviewed as mentioned in the Investigator Initiated Multisite Trial SOP.

11.5 Site Communication

When all participating institutions have successfully received IRB approval *and* have started enrolling patients, teleconferences to discuss participants and study-related matters will be held at least every two months, although calls may occur more frequently if needed. Teleconferences will be coordinated by Research staff at a participating institution; PIs, Research Coordinators, Nurses, and Co-Investigators if needed will participate. Any issues with patient compliance, database entry, or other items will also be discussed in these calls. Calls may include review by PIs of subject data to assure validity as well as the safety of subjects; and the progress of the trial may also be discussed. At times of study renewal or more frequently if needed, PIs may review safety reports and clinical trial efficacy endpoints and confirm that the safety outcomes favor continuation of the study.

10. STATISTICAL CONSIDERATIONS

10.1 Statistical Design

The proposed research is a RCT with a primary aim of determining if a mobile application may enhance adherence to swallowing therapy in patients undergoing radiation for head and neck cancer thus improving swallowing outcomes. Analysis of the primary endpoint (adherence) will be carried out using logistic regression, comparing arms A and B. A secondary endpoint will be the average percent adherence per week. Analysis of the secondary adherence endpoint will be carried out using a linear mixed effect model with weekly adherence as a dependent variable, a patient-specific random intercept, treatment arm as the primary predictor, and week as a fixed (categorical) effect. We will also explore the impact of the mobile app on a variety of swallowing outcomes including diet level, patient perception, and physiological measures. Analysis of these endpoints will be carried out using logistic regression comparing arms A and B.

(x) Randomization

Randomization will be carried out using pre-printed lists with block size of 4.

10.4 Primary Analysis

Analysis of the primary endpoint (adherence) will be carried out using logistic regression, comparing arms A and B. Analysis of the secondary adherence endpoint will be carried out using a linear mixed effect model with weekly adherence as a dependent variable, a patient-specific random intercept, treatment arm as the primary predictor, and week as a fixed (categorical) effect.

(y) Analysis Population

Analysis will include all participants.

(z) Analysis Plan

As above

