We have developed a demographic information instrument to allow us to properly describe our cohort and to examine possible effects of these factors on adherence and functional outcome measures. (Appendix L) Variables of interest include age, sex, ethnicity, disease stage, disease site, HPV status, education level, marital status, distance from home to treatment center, and insurance status. Additionally, participants will be asked to rate their comfort level with smartphone technology using a visual analogue scale (Appendix C). These will be completed at the time of study enrollment, prior to randomization.

Participants will be asked to complete and log their swallow exercises using either the Vibrent application or paper forms throughout the duration of radiation therapy. The Vibrent application will time stamp the date and time of data entry for secondary analysis to determine whether logging occurs on a daily basis or in batch. Paper logs will be collected by study personnel and entered into a central Redcap database. Each patient's program will ask the patient to complete 3 sets of ten repetitions of four different exercises, twice each day: Jaw stretches, Effortful Swallow, Mendelsohn Maneuver, and the Masako Maneuver. These maneuvers have all been well described and validated in the literature for patients undergoing treatment for head and neck cancer (Pauloski 2008).

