Participants in the paper control group (Group B) will be asked to log exercises on provided logging sheets (Appendix D). Both groups will be asked to rate their pain on a scale of 1-10 daily when they log their exercises either on the control app or on their paper logging sheets. We acknowledge that there are limitations to relying on patient logging as a measure of adherence. Unfortunately, there is no gold standard for measuring exercise adherence. A number of patient reported surveys have been reported in the literature; however these have been shown to have limited reliability and validity (McLean 2017). In the absence of validated, reliable measures of adherence, patient logging remains the mainstay for measuring adherence in the majority of the exercise literature. The reliance on patient logging across treatment arms will minimize the risk for reporting bias in this study.

Aim 1: To evaluate the impact of the "HNC Virtual Coach" mobile application on patient adherence to a prescribed swallowing therapy protocol.

Primary outcome variable: Overall adherence to prescribed exercise protocol measured as percentage of prescribed exercises completed over a seven-week period. (i.e. if participants are asked to complete 6 sets of 10 reps of each exercise daily for 7 weeks, maximum potential would be 420 sets).

Aim 2: To evaluate the impact of the "HNC Virtual Coach" program on the prevalence, characteristics, and severity of dysphagia in patients undergoing radiation therapy for head and neck cancer.

Secondary outcome variables:

Patient reported:

MD Anderson Dysphagia Inventory (MDADI) (Appendix E)

Clinician reported:

Functional Oral Intake Score (FOIS) (Appendix F)

Performance Status Scale – Head and neck (PSS HN) (Appendix G)

Functional measures obtained during videofluoroscopic swallowing studies (VFSS):

Penetration Aspiration Scale (PAS) (Appendix H)

Individual item and composite scores of the Modified Barium Swallow Impairment Profile (MBS-ImP) (Appendix I)

Dynamic Imaging Grade of Swallowing Toxicity (DIGEST) severity scores (Appendix J) Maximal interincisor distance

See study calendar for when these outcome measures will be collected

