8.1 Primary Outcome Measure

Adherence to prescribed exercise protocol

(a) 8. 1.2 Measurement Definition

Overall adherence to prescribed exercise protocol measured as percentage of prescribed exercises completed over a seven-week period. (i.e. if participants are asked to complete 6 sets of 10 reps of each exercise daily for seven weeks, maximum potential would be 420 reps).

(b) 8.1.3 Measurement Methods

Participants will be asked to complete and log their swallow exercises using the either the Vibrent application or paper forms throughout the duration of radiation therapy and for 1 month after the completion of therapy. The Vibrent application will time stamp the date and time of data entry for secondary analysis to determine whether logging occurs on a daily basis or in batch. Paper logs will be collected by study personnel weekly and entered into a central Redcap database.

(c) 8.1.4 Measurement Time Points

Adherence measures will be obtained at the conclusion of the 7-week treatment period.

8.2a Secondary Outcome measures (These measures, in combination, provide a comprehensive evaluation of swallowing physiology, its functional impact, and patient perception.)

Patient reported:

MD Anderson Dysphagia Inventory (MDADI)

(d) 8.2a.2 Measurement Definition

The MD Anderson Dysphagia Inventory (MDADI) was selected to capture and quantify the patient perception of swallowing dysfunction. It is a 20-item patient reported survey that

measures the impact of dysphagia on patients with HNC. Each item is scored on a 5 point scale with 1=lower function and 5=higher function. Possible scores range from 20-100 with higher scores indicating more normal swallowing function. Mean scores will be assessed for each treatment group at the time of each assessment. Standard deviation and 95% CI will be reported.

(e) 8.2a.3 Measurement Methods

MDADI: Each item is rated on a scale of 1-5 with lower numbers indicating poorer function. Mean subscale scores are multiplied by 20 to provide a final score between 20-100. All participants will complete on paper forms.

(f) 8.2a.4 Measurement Time Points

Please see study schedule for the measurement time points.

8.2b Secondary Outcome measure

Functional Oral Intake Score (FOIS)

(g) 8.2b.2 Measurement Definition

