12.6 Sample Size

(cc) 12.6.1 Accrual estimates

Accrual estimates are based upon average clinical volumes at three participating institutions over the past 3 years.

(dd) 12.6.2 Sample size justification

88 patients will be enrolled in each arm. This number will provide 80% power to detect a 15 percentage point difference between groups. This sample size includes the addition of 20% to account for anticipated drop out.

(ee) 12.6.3 Effect size justification

This calculation is made assuming 33% adherence in arm B and a standard deviation of 32 based on prior studies.

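### The primary endpoint is a percentage and 88 per arm is sized on means, but the primary test is an unspecified logistic regression, so the stated 80% power cannot be tied to it

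*Combined protocol and SAP*

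**What the plan says.** Section 8.1.2 defines the primary outcome as "Overall adherence to prescribed exercise protocol measured as percentage of prescribed exercises completed over a seven-week period". Section 4 (Aim 1) and the opening of Section 8 define it in the same way. None of them sets a threshold above which a patient counts as adherent.

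Section 10.4 states: "Analysis of the primary endpoint (adherence) will be carried out using logistic regression, comparing arms A and B". The synopsis and 10.1 say the same, and the analysis-plan heading under 10.4 only refers back to that sentence. A model on the percentage scale is given only for the secondary endpoint: "Analysis of the secondary adherence endpoint will be carried out using a linear mixed effect model with weekly adherence as a dependent variable".

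Section 12.6.2 says of 88 per arm: "This number will provide 80% power to detect a 15 percentage point difference between groups", after adding 20% for dropout. Section 12.6.3 adds: "This calculation is made assuming 33% adherence in arm B and a standard deviation of 32 based on prior studies". Neither alpha nor sidedness is stated anywhere.

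**The concern.** Ordinary logistic regression needs a binary outcome, and this endpoint is a number from 0 to 100 for each patient. The sizing inputs (a mean, a difference in points and a free-standing SD) belong to a comparison of means. The test that decides the trial and the calculation that justifies its size therefore do not refer to the same analysis.

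Someone will have to choose what logistic regression means here, possibly after data are in hand. Section 11.5 lets site investigators look at efficacy endpoints at study renewal, so an open cut-off is a practical risk. The candidate readings differ in power and in validity. All of them yield an odds ratio, whereas the trial is sized on a difference of 15 percentage points.

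**Working it through.** **Inputs.** Difference 15 points, SD 32 points, arm B mean 33%, power 80%, 20% added for dropout, 88 per arm (synopsis, 12.6). Assumed: two-sided alpha 0.05.

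**1. Reproduce 88.** Normal approximation: n = 2(1.960 + 0.842)² × (32/15)² = 2 × 7.85 × 4.55 = 71.4, so 72 per arm. The exact t calculation gives 72.4, so 73. Then 73 × 1.2 = 87.6, so 88, an exact match.

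Alternatives that do not lead to 88:
- One-sided 5% means: 57 per arm, × 1.2 = 69.
- Two proportions, 33% v 48%, two-sided: 167 per arm, × 1.2 = 201.

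Losing 20% of 88 leaves 70 evaluable (88 × 0.8 = 70.4). Power of the t-test is 78.6% at 70, 80.3% at 73 and 87.1% at 88.

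**2. Reading (a): dichotomise each patient.** The cut-off is not given, so a distribution must be assumed. With k = μ(1−μ)/SD² − 1, a beta distribution with SD 0.32 has parameters (0.383, 0.777) at mean 0.33 and (0.690, 0.748) at mean 0.48. A normal distribution with the same means and SD is a second shape. Power from the two-proportion formula, two-sided 5%:

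| Cut-off | Responders B v A (beta) | Beta: n = 70 / 73 / 88 | Normal: n = 70 / 73 / 88 | n per arm for 80% (beta) |
|---|---|---|---|---|
| 25% | 0.474 v 0.686 | 72 / 74 / 82% | 56 / 57 / 65% | 85 |
| 50% | 0.300 v 0.475 | 57 / 58 / 67% | 58 / 60 / 68% | 121 |
| 75% | 0.159 v 0.270 | 36 / 37 / 43% | 42 / 43 / 50% | 214 |
| 80% | 0.131 v 0.227 | 31 / 32 / 38% | 37 / 38 / 45% | 254 |

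Simulating the logistic Wald test under the beta assumption (20,000 runs, 73 per arm) agrees closely: 80% at a 10% cut-off, 75% at 25%, 59% at 50%, 41% at 70% and 31% at 80%.

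If 33% and 48% are themselves read as proportions of adherent patients, power is 44% at 70, 45% at 73 and 53% at 88.

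If the cut-off is chosen after seeing the data, the simulated type I error at 73 per arm is 11.5% with three candidates (25, 50, 75%) and 20.0% with nine (10% to 90% in steps of 10).

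**3. Reading (b): treat completed sets as independent binomial trials.** The model's SD for one patient's proportion is √(0.33 × 0.67/m), against the plan's own between-patient SD of 0.32. The ratio 0.32/√(0.2211/m) is the factor by which the standard error is too small. The null rejection rate is 2[1 − Φ(1.96/ratio)].

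| m | Source | Ratio | Type I error |
|---|---|---|---|
| 294 | 6 sets × 49 days, one exercise | 11.7 | 87% |
| 420 | the documents' stated maximum | 13.9 | 89% |
| 1,176 | 294 × 4 exercises | 23.3 | 93% |

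Simulation at 73 per arm gives the same rates (0.867, 0.888, 0.933). The denominator is itself unsettled. Section 4 says "maximum potential would be 420 sets", Section 8 gives the same number as repetitions, and the prescription in Section 4 is to "complete 3 sets of ten repetitions of four different exercises, twice each day", which yields 294 sets per exercise over 49 days. These statements need to be reconciled.

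**4. Reading (c): fractional logit of the percentage with robust standard errors.** Under the same beta assumption, simulated power is about 78% at 70, 80% at 73 and 87% at 88, with type I error about 5%. This is essentially the t-test's performance.

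**The case against.** The strongest reply is that reading (c) is a legitimate logistic regression for a percentage and keeps the intended power, so the plan is under-specified and not shown to be underpowered. That is correct, and the conclusion goes no further. But nothing in the plan points to a fractional logit, and the ordinary meaning of logistic regression requires a binary outcome that the endpoint does not supply.

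Three further points have merit:
- Power at low cut-offs depends on the assumed shape: at 25% and 73 per arm it is 74% under the beta and 57% under the normal. With all 88 per arm analysed, the beta gives 82%. The shortfall at 50% and above appears under both shapes and at all three sample sizes.
- The plan does not propose an uncorrected binomial model or a search over cut-offs. Those figures show what the wording leaves open, not what the sponsor intends.
- The secondary mixed model has arm and categorical week without an interaction. With complete weekly data and equal weekly prescriptions, its arm coefficient equals the seven-week mean difference in points. An estimate on the sizing scale therefore exists, but it is labelled secondary and does not decide the trial.

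The session thresholds in the feasibility results (Section 2.3) are background and are not adopted as a responder definition.

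**Conclusion.** The concern holds and should be fixed before any comparison of the arms. The endpoint is continuous, 88 per arm matches a comparison of means exactly, and the named primary test has no form that connects it to either. Among readings with a valid error rate, power at 73 per arm runs from about 80% (fractional logit) to about 31% (80% cut-off). A post-hoc cut-off raises type I error to roughly 11–20%, and an uncorrected binomial model raises it to roughly 87–93%.

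The reproduction of 88 rests on an assumed two-sided 5% alpha. The responder powers rest on assumed distributions and serve only to show the range. The mismatch between endpoint, sizing and test needs neither distribution.

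**What to change.** In the synopsis, 10.1 and 10.4, replace logistic regression for the primary endpoint with a linear model (or two-sample t-test) of seven-week percent adherence on arm. Report the mean difference in percentage points with its 95% CI, and state alpha and sidedness. Robust standard errors and a site covariate are optional. This is the analysis that 88 per arm was sized for.

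If a logistic model is preferred, specify before any arm comparison either a fractional logit with robust standard errors or one fixed responder cut-off. Then restate power for that choice at the evaluable sample size (about 70 per arm after 20% loss).

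Cost: a wording change in three places, processed under 11.2: "Any changes made to the protocol will be submitted as a modification and will be approved by the IRB prior to implementation". That section also gives participating investigators 90 days to obtain IRB approval. The linear model or fractional logit needs no new data or patients. A fixed cut-off of 50% would need about 121 evaluable per arm under the beta assumption, and higher cut-offs would need more.
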